Clinical Efficacy Analysis of Resveratrol in the Treatment of Primary Ovarian Insufficiency

Date: May 16, 2022

Research Proposal Summary

Scheme number	LCYJ-B05
Scheme name	Clinical effect of resveratrol on early onset ovarian insufficiency
Version number/date	Version 2.1, May 16, 2022
Indications	POI
Test purpose	In order to evaluate the role of resveratrol in the occurrence and development of a variety of ROS-related diseases including POI/POF, and to clarify the clinical effect and mechanism of resveratrol antioxidant therapy.
Research design	Prospective, multicenter, randomized, controlled clinical trial design
Total number of cases	150
Number of research centers	4
Study period	36 months
Research object	Diagnostic criteria : The diagnostic criteria for premature ovarian insufficiency (POI) refer to the “2017 Chinese Expert Consensus on Clinical Diagnosis and Treatment of Premature Ovarian Insufficiency” and “2016 Expert Consensus on Hormone Supplementation Therapy for Premature Ovarian

Insufficiency”; including: (1) Age <40 years old; (2) oligomenorrhea or amenorrhea for at least 4 months; (3) at least 2 times serum basal follicle-stimulating hormone (FSH) >25IU/L (interval > 4 weeks). Subclinical POI: FSH level is 15~25 IU/L, which is a high-risk group.

The diagnostic criteria for premature ovarian failure (POF) refer to the “2017 Chinese Expert Consensus on Clinical Diagnosis and Treatment of Premature Ovarian Insufficiency”, which refers to amenorrhea, FSH>40IU/L, and decreased estrogen levels before the age of 40, accompanied by varying degrees of perimenopause Stage symptoms are the terminal stage of POI.

standard constrain:

1. Amenorrhea or oligomenorrhea at least 4 months and two (>4 weeks interval) basal FSH \geq 10mIU/ml;
2. age<40 years old;
3. Informed consent, voluntary experiment.

Exclusion criteria:

1. Pregnant and lactating patients;
2. Patients with endometriosis, adenomyosis, endometrial lesions (submucosal fibroids ,endometrial polyps, etc.) , uterine fibroids>4 cm or hysterectomy;
3. Patients with adrenal cortical hyperplasia or tumor;
4. Ovarian neoplasms patients;
5. Hydrosalpinx patients;
6. Hyperprolactinemia patients;
7. Patients who are participating in other clinical trials or

	
have participated in other clinical trials within the past three months;
 
8. Patients with suspected or real history of alcohol and drug abuse;
 
9. Known allergy to the investigational drug or its components;
 
10. Other patients deemed unsuitable for participation in this trial by the investigator.
 
Note: Patients who were receiving hormone replacement therapy at the time of recruitment were required to take at least a 3-month suspension of medication to participate in this trial.

Trial grouping and medication
	
1. POI patients group: According to the computer-generated random sequence, eligible patients were randomly assigned to the RES group and non-RES group according to 1: 1. POI IVF patients were divided into two groups: the RES treatment group (group A) and the non-RES treatment group (group B). Basal sex hormone and anti-Muller tube hormone were administered on day 2/3 of the menstrual cycle before treatment and 3 months after treatment. Antral Follicle (AFC) was detected by transvaginal B-ultrasonography, and basic sex hormones included follicle-stimulating hormone (FSH), Luteinizing hormone (LH), Estradiol 2 (E₂) and Testosterone (T).
 
2. Medication: Patients in group A received oral RES at 250mg daily for three months, and those in the non-RES group received oral vitamin E at 100mg daily for three months.

Treatment and follow-up
	
Course of treatment: Patients in group A received oral RES at 250mg daily for three months, and those in the non-RES group received oral vitamin E at 100mg daily for three months. All patients used microstimulation to superstimulate ovulation, and

clomiphene 50-150mg was taken orally from the 3rd to 5th day of menstruation, once a day for a total of 5 days later, the sex hormones and follicular diameter were checked, and 150-300IU Gonadotropin (Gn) was added as appropriate to the night needle day. After follicle maturation, 10000IU of Human Chorionic Gonadotropin (HCG) was injected intramuscularly or 250ug Ovidrel subcutaneously to induce ovulation. 36-38 hours later, a vaginal ultrasound-guided puncture was performed to collect eggs.

Specific inspection items include:

1. The patient's hormone levels (basal FSH, LH, E2, T) were detected on day 2/3 of the menstrual cycle;
2. Anti-Mullerian hormone (AMH) was detected in patients on day 2/3 of the menstrual cycle;
3. The numbers of antral follicles (AFC) were recorded by B ultrasound transvaginal;
4. Pregnancy was recorded at the outpatient follow-up for patients with reproductive needs ;
5. Patients were routinely tested for blood routine (RBC, WBC, PLT, HGB), liver function (ALT, AST) and renal function (BUN, Cr), and recorded adverse events.

Note:

1. Basal follicle-stimulating hormone (FSH) $\geq 10\text{mIU/ml}$ at the first visit, and if other inclusion criteria are met if the patient has a history of testing with a baseline FSH $\geq 10\text{mIU/ml}$ in the past (interval > 4 weeks), he or she can be included in this study and drug therapy can be started; (Interval > 4 weeks) If the basic FSH $\geq 10\text{mIU/ml}$ has not been diagnosed, the patient is required to visit the hospital again after 4 weeks. If the basic FSH is still $\geq 10\text{mIU/ml}$, they can be included in this study and drug therapy

	
can be started.
 
2. For patients with regular menstrual periods, the basal FSH and antral follicle count (AFC) should be followed up on the 2nd to 4th day of the menstrual cycle. If the patient has menstrual cramps after the follow-up and has not exceeded the visit window, they are required to re-examine on the 2nd to 4th day of the menstrual cycle and record the examination data.

Study endpoint	
Primary endpoint : FSH, LH
 
Secondary endpoints :
 
(1) FSH, LH, E₂, T; (2) Antral follicle count (AFC); (3) Basal sex hormones and Anti- Mullerian hormone (AMH) on day 2/3 of the menstrual cycle; (4) Embryo laboratory indicators including number of eggs harvested, number of MII eggs, normally fertilized number, and number of good quality embryos; (5) Peripheral blood human villous gonadotropin (HCG); (6) Clinical pregnancy rate (patients with reproductive needs).

Security indicators	
1. Blood routine (RBC, WBC, PLT, HGB) , liver function (ALT, AST) and renal function (BUN, Cr) ;
 
2. Patient adverse events were recorded.

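### Women enter at FSH of 10 or more, but the protocol's POI definition needs FSH above 25 twice, and no planned result shows whether the pooled effect applies to POI

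*Protocol*

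**What the plan says.** Under Research object, the protocol's diagnostic criteria require, for POI, "at least 2 times serum basal follicle-stimulating hormone (FSH) >25IU/L (interval > 4 weeks", together with age and menstrual conditions. The next sentence adds "Subclinical POI: FSH level is 15~25 IU/L, which is a high-risk group". Premature ovarian failure (POF), described as the end stage of POI, has FSH above 40 IU/L with amenorrhea and low estrogen.

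Inclusion criterion 1, in the same section, admits women with "Amenorrhea or oligomenorrhea at least 4 months and two (>4 weeks interval) basal FSH \geq 10mIU/ml". Note 1, under the inspection items, applies the same threshold. It accepts a past test as one of the two values, and for women without one it says of the repeat visit: "If the basic FSH is still $\geq 10\text{mIU/ml}$, they can be included in this study". None of the ten exclusion criteria refers to FSH.

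The label is POI throughout. The title is "Clinical Efficacy Analysis of Resveratrol in the Treatment of Primary Ovarian Insufficiency", the indication is POI, and the allocation paragraph opens "POI patients group: According to the computer-generated random sequence, eligible patients were randomly assigned". Only the test purpose is wider: it speaks of "a variety of ROS-related diseases including POI/POF".

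FSH and LH are the primary endpoints. The SAP names a full analysis set, a per-protocol set and a safety set, with repeated measures analysis of variance, Bonferroni comparisons and chi-square tests. It mentions no FSH category, no baseline covariate and no interaction.

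**The concern.** The age and menstrual conditions for entry match those in the POI definition, so FSH is where the two part. The entry rule reaches below both the POI and the subclinical range, and everyone who enters is then called POI. A pooled result could be reported as efficacy in POI although an unknown share of the sample does not meet the protocol's definition of it.

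FSH is both the entry variable and a primary endpoint. A reader who wants to know whether the result holds for POI as defined would need to see the effect by baseline FSH, and nothing planned would show it.

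**Working it through.** **Step 1: one scale.** 1 mIU/ml is 1000 mIU per litre, which is 1 IU/L. The thresholds compare directly, and notation does not explain the gap.

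**Step 2: the thresholds side by side.** The entry floor of 10 lies 25 − 10 = 15 below the POI cut-off and 15 − 10 = 5 below the subclinical floor.

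| Two qualifying FSH values | Admitted by criterion 1 and Note 1 | Class under the diagnostic criteria |
|---|---|---|
| both 10 to <15 | yes | none |
| both 15 to 25 | yes | subclinical POI only |
| both >25 | yes | POI (POF needs >40 and further signs) |
| discordant, e.g. 12 and 18, or 22 and 28 | yes | not POI; otherwise ambiguous |

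The last row is ambiguous because the POI definition demands two tests, while the subclinical definition gives no number of tests.

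**Step 3: is the entry threshold a slip?** Note 1 states the threshold of 10 four times as a working rule, so it is not a stray typing error.

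**Step 4: what the pooled effect would mean.** The documents give neither the FSH mix nor any effect by category, so this is a range under assumptions. Let p be the share of women without both values above 25, and r their effect relative to women with both above 25, additive on one scale. Then pooled effect / POI effect = 1 − p + r·p.

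| p | r = 0 | r = 0.5 | r = 1 | r = 1.5 |
|---|---|---|---|---|
| 10% | 0.90 | 0.95 | 1.00 | 1.05 |
| 25% | 0.75 | 0.88 | 1.00 | 1.13 |
| 50% | 0.50 | 0.75 | 1.00 | 1.25 |

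The pooled effect could understate, match or overstate the effect in POI.

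**Step 5: precision of estimates by category.** Inputs: 150 women and 1:1 allocation (protocol summary); assumed: a common SD and 1:1 within each category. Interval width relative to the pooled interval is 1/√(1−p) for women with both values above 25, 1/√p for all others, and 1/√(p(1−p)) for the difference between the two.

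| p | Both >25 (women) | All others (women) | Difference |
|---|---|---|---|
| 10% | 1.05 (135) | 3.16 (15) | 3.33 |
| 25% | 1.15 (about 112) | 2.00 (about 38) | 2.31 |
| 50% | 1.41 (75) | 1.41 (75) | 2.00 |

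The common SD matters. If the SD among all others were half the pooled SD, their interval at p = 25% would be 0.5 × 2.00 = 1.00 times the pooled width.

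**Step 6: gain from a baseline covariate.** The protocol already schedules the hormones: "Basal sex hormone and anti-Muller tube hormone were administered on day 2/3 of the menstrual cycle before treatment and 3 months after treatment". Assume two time points, arm and time as factors, equal variance σ² at both times, and correlation ρ between them. The arm-by-time test is then a comparison of change scores, with variance proportional to 2σ²(1−ρ). With the baseline value as covariate it is proportional to σ²(1−ρ²). The ratio is (1+ρ)/2. For assumed ρ of 0.3, 0.5 and 0.7 this is 0.65, 0.75 and 0.85, so the interval is 0.81, 0.87 and 0.92 times as wide.

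**The case against.** The best defence is that the wide entry is intended. The threshold of 10 recurs consistently, the test purpose extends beyond POI, and the diagnostic section itself singles out subclinical women as high-risk. An all-randomised analysis without subgroups is not a statistical error. All of this stands, and it rules out treating the threshold itself as a mistake. It does not settle the label: no text says that women below the POI definition are the intended population, and the title and indication are not adjusted.

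A second objection is that the figures in Steps 4 and 5 carry no information from this trial. That is right. The first range also needs an additive effect: if the effect on FSH were proportional, raw-scale effects would differ by baseline even with equal percentage effects. The figures show only that the direction is open and what precision to expect.

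Third, the covariate is a separate matter from the label. Agreed; it is proposed as a precision gain only.

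A reader might infer more than the documents support:

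- **That the comparison is biased or loses power.** All eligible women are randomised under one rule, so the comparison is valid for them. The documents give no SD, effect size or FSH mix, so no loss of power can be shown.
- **That discordant pairs have no class.** The subclinical definition states no number of tests, so a pair with one value in its range is ambiguous rather than excluded.
- **That a historical qualifying value goes unrecorded.** The case report form is not among the documents, and Note 1 already requires that value and its interval to be checked at entry.

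**Conclusion.** The point holds as a mismatch between the population admitted and the population named, and it should be fixed. That part rests on the text alone. Women with both values from 10 to <15 fit no FSH definition in the protocol, women with both from 15 to 25 are subclinical only, and the SAP plans nothing that would show whether a pooled effect applies to POI as defined.

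Its size is not determinable. The number of women concerned is unknown, and women with lower FSH could respond less, equally or more. If they respond equally, only the labelling problem remains.

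**What to change.** 1. Reconcile the diagnostic criteria, inclusion criterion 1, Note 1 and the population label. The sponsor states which threshold is intended. If the wider entry is kept, the title, indication and conclusion should describe women with elevated FSH, including POI.
2. Keep the all-randomised comparison as primary, and analyse 3-month FSH and LH each with the pre-treatment value of the same hormone as covariate. No new measurement is needed.
3. Report baseline counts by FSH category: 10 to <15, 15 to 25, and >25 with >40 shown separately, plus discordant pairs. The >40 row is a count by FSH only, since POF has further conditions.
4. Pre-specify, as supportive evidence, the treatment effect with confidence intervals in women with both qualifying values above 25 and in all others. Add a treatment-by-baseline-FSH interaction with its interval on a stated scale, raw or log. State that a non-significant interaction is not to be read as equal effects, and word any POI-specific conclusion accordingly.

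The cost is protocol wording and about one SAP paragraph. Classifying women by the two-test rule needs both qualifying values to hand, and a historical one may have to be retrieved from records. The sample size and the groups compared in the primary analysis do not change. The drawback is the imprecision of the category estimates shown in Step 5, which is why they are supportive only.

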Clinical Efficacy Analysis of Resveratrol in the Treatment of Primary Ovarian Insufficiency

Date: May 16, 2022

Research Proposal Summary

Statistical analysis

The case observation form completed by the test center was reviewed and returned by the project team of Reproductive Medicine Center, Affiliated Hospital of Nantong University, and the data was processed by a statistical analyst. The data in the case report form is entered in two copies, and the database is locked after verification and confirmation. SPSS26.0 software was used for statistical analysis. The full analysis set (FAS) and the per-protocol set (PPS) were used for effectiveness analysis, and the safety data set (SS) was used for safety analysis. Measurement data were expressed as mean±standard deviation ($\bar{x}\pm s$), multiple time points were compared by repeated measures analysis of variance, and pairwise comparisons were by Bonferroni test; enumeration data were expressed by the number of cases or percentages, and χ^2 was used. Test for statistical comparison. $P<0.05$ indicated that the difference was statistically significant.

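### Entry requires two pre-treatment FSH readings, but the SAP neither defines baseline FSH nor gives the second reading a role; using both as covariates would be a cheap gain in FSH precision.

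*Protocol*

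**What the plan says.** Inclusion criterion 1 in the protocol summary requires "Amenorrhea or oligomenorrhea at least 4 months and two (>4 weeks interval) basal FSH" of at least 10 mIU/ml.

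Note 1, under the inspection items, gives two ways to meet this. A first-visit value in range is enough "if the patient has a history of testing with a baseline FSH" in range more than 4 weeks apart. Otherwise "the patient is required to visit the hospital again after 4 weeks", and she enters if the value is still in range. On both routes drug therapy starts only after the second qualifying value is available.

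The section on trial grouping and medication schedules the sex hormones and AMH on day 2/3 of the cycle "before treatment and 3 months after treatment". The endpoint section reads "Primary endpoint : FSH, LH".

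In the SAP, "multiple time points were compared by repeated measures analysis of variance", with Bonferroni pairwise comparisons. It does not define baseline, does not say which qualifying reading is the pre-treatment value, and names no covariate.

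**The concern.** FSH is a named primary endpoint, and 150 women at 1:1 give 75 per arm. No effect size, SD or power is stated, so the margin is unknown. A single FSH value measures a woman's underlying level with error, and a second pre-treatment value carries further information about it. Both readings are needed for eligibility and precede treatment, so using them as covariates cannot bias the comparison between arms. It can only sharpen it, provided no women are lost from the analysis.

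Two things are at stake. One is precision on FSH that needs no extra visit or sample. The other is that, with baseline undefined, the choice of which reading counts as the pre-treatment value stays open until the data are in hand.

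**Working it through.** **Inputs from the documents.** Two FSH readings of at least 10 mIU/ml, more than 4 weeks apart (inclusion criterion 1, Note 1); one scheduled pre-treatment time and one at 3 months (trial grouping and medication); 150 women, 1:1; P<0.05 (SAP).

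**Inputs assumed.** The correlation r between FSH readings (its reliability), the log-scale SD and the median FSH; none is given. Readings have equal variance, and the test is two-sided.

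**The plan's own figure.** The total of 150 cannot be reproduced, because no design inputs are stated. For orientation, 75 per arm at 80% power detects (1.960 + 0.842) × √(2/75) = 0.46 SD on the 3-month value alone, before dropout.

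**Closed form, no selection on entry values.** Variance per woman, in units of the FSH variance:

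- Change from one reading: 2(1 − r). With two time points, the group-by-time test of the planned ANOVA is this comparison.
- ANCOVA on one reading: 1 − r².
- ANCOVA on two comparable readings: 1 − 2r²/(1 + r).

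| r | Change score | ANCOVA, one | ANCOVA, two | Two vs one |
|---|---|---|---|---|
| 0.5 | 1.000 | 0.750 | 0.667 | 0.889 |
| 0.7 | 0.600 | 0.510 | 0.424 | 0.830 |

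An effect with 80% power under one-baseline ANCOVA would have 84.4% (r = 0.5) or 86.7% (r = 0.7) with two readings.

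**Selection on both readings.** Entry truncates both readings at 10, which weakens their correlation. The simulation used log FSH with assumed median 22 and log SD 0.7, both readings at least 10, a third reading as outcome, and 2 million draws per setting. Equivalent N is 150 divided by the ratio.

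| Reliability | Residual variance, two vs one baseline | Equivalent N |
|---|---|---|
| 0.4 | 0.939 | 160 |
| 0.5 | 0.914 | 164 |
| 0.6 | 0.886 | 169 |
| 0.7 | 0.857 | 175 |
| 0.8 | 0.824 | 182 |

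That is a cut of 6-18%. At reliability 0.6, medians of 15-35 and log SDs of 0.5-0.9 give 9.5-14%.

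**Old historical reading.** At reliability 0.6, with true levels correlated 0.5, 0.7 and 0.9 between the historical date and entry, the ratios are 0.982, 0.960 and 0.919: a cut of 2-8%. From a starting power of 80%, that means about 81-83%.

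**Against the planned change score.** In the same simulation, ANCOVA with both readings has 25-29% less variance than the change score for reliability 0.4-0.8. With an old reading it has 17-23% less, at reliability 0.6. Much of this comes from ANCOVA itself. In the closed form at r = 0.5, one-baseline ANCOVA alone takes 1.000 to 0.750 (25%), and the second reading takes 0.750 to 0.667 (a further 11%).

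**Why not a plain average.** Suppose the historical reading has half the correlation (r/2) with both other readings. The variance of change from the mean of the two is then 1 + (1 + r/2)/2 − 1.5r. At r = 0.7 this is 0.625 against 0.600, or 4% more; at r = 0.8 it is 0.500 against 0.400, or 25% more. As a separate covariate, the same reading still gives a cut of about 2%.

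**The case against.** A reader might infer that the plan discards the second reading. The documents do not say so. The SAP is silent, and its reference to several time points does not exclude a second pre-treatment value. What can be shown is that baseline is undefined and the reading has no stated role.

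A reader might also assume that a good second value is already in hand for everyone. Note 1 does not guarantee that. The historical route sets no limit on age, laboratory or assay and does not require the number to be recorded. Nothing says the value must post-date a suspension of hormone replacement. Only the 4-week repeat is sure to be taken for the study, and the split between routes is unknown. If half the women had a repeat and only those repeats were used, the ANCOVA gain would average about 6-8% at r = 0.5-0.7. The lower range of 2-8% is therefore as plausible as 6-18%.

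The 6-18% is also measured against a one-baseline ANCOVA that the SAP does not plan. This stands, and it is why the comparison with the change score is given separately.

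Finally, it is tempting to say that an extra covariate can never hurt. That fails under complete-case analysis: dropping 3 of 150 women cancels a 2% gain (150 × 0.02 = 3), and dropping 12 cancels an 8% gain (150 × 0.08 = 12). A rule for missing values is an essential part of the proposal.

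**Conclusion.** The point holds as a cheap improvement. Two pre-treatment FSH readings are required, one pre-treatment time is scheduled, and the SAP neither defines baseline FSH nor uses the other reading. The second reading is worth about 6-18% of FSH residual variance beyond one-baseline ANCOVA if comparable, and about 2-8% if it is an old historical result. The full move from the planned change-score comparison is worth about 25-29%, or about 17-23% with an old reading, part of it due to ANCOVA alone. All of these rest on an assumed median, SD and reliability.

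Two stronger readings are not supported. The omission does not bias the comparison or invalidate the result. Nor does the gain cover the whole primary endpoint: the two-reading rule concerns FSH, no second LH reading is required, and no benefit for LH has been shown.

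**What to change.** In the SAP:

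- Define baseline FSH as the reading closest before treatment.
- Analyse 3-month log FSH by ANCOVA, with treatment arm and both pre-treatment readings as separate log-scale covariates, not their plain average.
- State when an earlier reading counts as not comparable (by age, laboratory or assay), before any outcome data are seen by arm.
- Pre-specify a missing-indicator or baseline-imputation rule for an earlier value that is missing or not comparable, so that no randomised woman is dropped.
- State that the second-reading gain is claimed for FSH only.

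In the case report form, record value, date and laboratory for both qualifying FSH readings. Sites must already see the earlier result to apply Note 1.

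The cost is a few data fields, one extra covariate (plus an indicator, if that rule is chosen) and a short paragraph in the SAP. No extra patients, visits or samples are needed.

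### The four-centre plan states no stratification by centre and analyses without a centre factor, which can cost precision on some endpoints

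*Protocol*

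**What the plan says.** The Research Proposal Summary of the protocol gives the design as "Prospective, multicenter, randomized, controlled clinical trial design", with "Total number of cases 150" and "Number of research centers 4". Under Trial grouping and medication, the whole account of allocation is that "According to the computer-generated random sequence, eligible patients were randomly assigned to the RES group and non-RES group", at 1:1. The number of lists, any blocking and any stratification factor are not mentioned. Patients per centre are not given.

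Under Study endpoint the entry is "Primary endpoint : FSH, LH". The secondary endpoints include AFC, AMH, egg and embryo counts and clinical pregnancy. Hormones, AMH and AFC are measured before treatment and at 3 months. The egg, embryo and pregnancy outcomes have no pre-treatment measurement.

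The Statistical analysis section of the SAP says that "multiple time points were compared by repeated measures analysis of variance", with Bonferroni pairwise comparisons, and names a chi-square test for counts. It names no centre factor, stratification factor or other covariate. It does not say which ANOVA effect is the test of treatment.

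**The concern.** Several outcomes depend on local staff and equipment: transvaginal follicle counts, egg maturity, fertilisation and embryo quality. No central laboratory or central reading is mentioned for any measurement. The stimulation text leaves part of the regimen to judgement, so practice may differ between centres before eggs are collected. FSH eligibility can rest partly on a past test, so case mix may differ too.

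If centre explains part of the outcome variance and is left out of the model, that part stays in the error term. The trial then behaves like a smaller one. If allocation is stratified by centre without the documents saying so, a model without centre overstates the standard error of the treatment difference.

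**Working it through.** The documents give no effect size, SD, power or between-centre variance, so there is no stated figure to reproduce.

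**Inputs.** From the protocol: 150 patients, 4 centres, 1:1, hence 75 per arm. From the SAP: significance level 0.05, taken as two-sided (assumption). Also assumed: the share of outcome variance due to centre (ρ), the centre sizes, and a complete outcome for every patient.

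**1. Detectable difference.** (1.96 + 0.84) × √(2/75) = 2.80 × 0.1633 = 0.457 SD at 80% power. This is solved back from the sample size and is not a planned effect.

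**2. Power with a centre term, single follow-up value.** The term multiplies the residual SD by √(1−ρ), so power = Φ(2.802/√(1−ρ) − 1.96). The equivalent sample size is 150 × (1−ρ). Where centres are not balanced between arms, the variance is inflated by about 1 + 3/145.

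| ρ (assumed) | √(1−ρ) | Power, balanced centres | Power, unstratified allocation | Equivalent N |
|---|---|---|---|---|
| 1% | 0.995 | 80.4% | 79.6% | 148.5 |
| 5% | 0.975 | 82.0% | 81.2% | 142.5 |
| 10% | 0.949 | 84.0% | 83.2% | 135 |
| 20% | 0.894 | 88.0% | 87.3% | 120 |

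The comparison is 80% without the term.

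**3. Which contrast is tested.** Each scenario was simulated 4,000 times, with assumed centre sizes 60/40/30/20 and a baseline-to-follow-up correlation of 0.5 within centre. Here the difference is 0.4575 within-centre SD. Adjusted power is therefore near 80% and unadjusted power falls below it, whereas step 2 fixes unadjusted power at 80%.

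| Outcome tested | Centre effect | Neither | Centre term only | Stratified only | Both |
|---|---|---|---|---|---|
| Follow-up value | 10% of level | 75.7% | 78.3% | 77.1% | 78.7% |
| Follow-up value | 20% of level | 69.5% | 78.4% | 71.9% | 80.6% |
| Change | 20% of level, stable over time | 79.3% | 78.9% | 78.9% | 78.3% |
| Change | 10% of change | 75.4% | 79.1% | 75.7% | 79.8% |

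Simulation error is about 0.7 points. A stable centre effect cancels within the patient, so the third row shows no gain. In the other rows most of the gain comes from the model term.

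**4. Type I error.** With neither change it was 4.6-4.9%. With stratified allocation and no centre term it fell to 3.2% (ρ = 10%) and 2.8% (ρ = 20%) for the follow-up value. Stratification removes between-centre variation from the treatment difference, but the unadjusted standard error still contains it. Simulation error is about 0.3 points.

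**5. Chance imbalance without stratification.** The chance that at least one centre splits 60:40 or worse depends on assumed centre sizes:

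| Centre sizes (assumed) | Overall 75:75 forced | Simple randomisation |
|---|---|---|
| 38/38/37/37 | 45% | 64% |
| 60/40/30/20 | 69% | 80% |
| 90/30/20/10 | 91% | 93% |

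The consequence is modest. In a centre of 38, such a split is 23:15, which is 23/75 = 30.7% of one arm and 15/75 = 20% of the other. If that centre is offset by 0.5 SD (assumed), the treatment difference moves by 0.107 × 0.5 ≈ 0.05 SD, against a standard error of 0.163 SD.

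**The case against.** A reader might infer that the trial uses one unstratified list across all centres. The documents do not say so. The allocation sentence is silent on the number of lists and fits blocked lists per centre equally well, and the protocol text is headed as a summary. What can be said is that stratification by centre is not stated.

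A reader might also infer that every endpoint loses precision. That does not follow. If treatment is judged by group-by-time, which repeated measures ANOVA at two time points allows, stable differences in assay or reader cancel and a centre term gains nothing. This objection stands for FSH, LH, AMH and AFC under that contrast. It does not cover outcomes without a pre-treatment value, or centres that differ in change, and the SAP leaves the contrast open.

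The size of the gain rests on assumed variance shares. At 1% it is negligible, and with unbalanced centres the term costs a fraction of a point. At 5% it is about two points. The primary endpoints are hormone levels, and if a central laboratory is used, one source of centre differences is removed. All of this limits the size of the problem. It does not remove the case for a term that costs so little.

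**Conclusion.** The point holds in a limited form. No stratification by centre is stated for a four-centre trial of 150, and the named analyses contain no centre factor. At 0.46 SD, with centre explaining an assumed 5-20% of outcome variance, adjustment raises power from about 80% to 82-88% when a single follow-up value is tested. A similar argument applies to change when centres differ in change. The figures are for a continuous outcome with all 150 patients. They were not worked out for pregnancy, which is recorded only in patients with reproductive needs.

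The centre term is worth having however allocation is done. Without stratification it recovers precision. With stratification it is needed to keep the test of follow-up values from being conservative.

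A reader might take the high chance of a 60:40 split in some centre to mean that the treatment comparison is biased. It is not: type I error stayed near 5% with neither change, because randomisation already accounts for chance imbalance. This is a matter of precision, worth correcting, and the trial's validity does not depend on it.

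**What to change.** 1. In the SAP, include centre as a fixed factor in the efficacy models for all continuous endpoints. If treatment is tested by group-by-time, centre must also enter with its interaction with time, because a centre main effect alone does not touch that contrast.
2. For clinical pregnancy, replace the plain chi-square test with a centre-stratified Cochran-Mantel-Haenszel test.
3. In the protocol, state whether allocation is stratified by centre, with block and concealment details. If recruitment has not started, use permuted blocks of varying size within each centre. If it has started, leave the allocation as it is and make only the analysis change.

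The model change costs about 3 error degrees of freedom (148 to 145 for a single follow-up value) and should be written in before outcome data are seen. Stratified allocation needs a new list for each centre. It adds less precision than the model term, so it is the lower priority of the two.
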